Aim 2: Assess feasibility, safety, acceptance, and impact on behavior and symptoms of *Anxiety Coach*. During Phase II, 30 therapists will participate in one of three trials to examine the feasibility of using *Anxiety Coach* to increase the frequency of exposure and improve outcomes with varying degrees of face-to-face contact: 1) Reviewing the acceptability of *Anxiety Coach* and integrating into their practice as desired (n= 30 therapists); 2) Treating children with anxiety disorders with treatment as usual or *Anxiety Coach* with face-to-face therapy, (N = 30 therapists and 30 patients); or 3) Treating children with anxiety disorders with treatment as usual or *Anxiety Coach* with minimal contact (N = 30 patients).

Note: The current modification covers the initiation of Trial 2 and Trial 3. Trial 1 has been approved and enrollment as begun.

Aim 3: Develop a protocol for implementing *Anxiety Coach*. During Phase III, the feasibility data, along with input from patients and therapists taking part in the research, will be analyzed and used to write a

treatment protocol for training therapists to use *Anxiety Coach* for augmenting face-to-face therapy and providing treatment with minimal direct contact.

When completed, this project will deliver a protocol detailing the use of an innovative smartphone technology, *Mayo Clinic Anxiety Coach*, to improve access to effective care for childhood anxiety disorders through 1) providing interventions outside traditional mental health settings with minimal provider contact; and 2) disseminating exposure-based CBT to community practitioners. These results will be used to pursue R01 funding to conduct randomized controlled trials powered to evaluate the symptom improvement and cost-efficiency of using *Mayo Clinic Anxiety Coach* in these settings. By increasing the reach and quality of treatment, *Anxiety Coach* has the potential to improve the outcomes for a large number of children suffering from anxiety disorders.

RESEARCH STRATEGY

Overview. This proposal satisfies the purpose of PAR-12-279 “Pilot Intervention and Services Research Grants (R34),” which seeks to encourage intervention development and service delivery research.

A. SIGNIFICANCE

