Trial 3. In Trial 3 (Increasing Access) children with anxiety disorders will be randomized to receive with MC-AC delivered by therapists in the Pediatric Anxiety Disorders Clinic (study staff) or treatment as usual in the community or within Mayo Clinic, just not with their current therapist. Data collection will include questionnaires completed by therapists, patients, and parents before and after treatment, as well as data automatically saved by the application. Following the study all patients will be offered treatment within the Pediatric Anxiety Disorders Clinic. Patients in the community treatment group will also receive the Anxiety Coach application.

C.3.c. Phase III: Revision Stage (4 months). During the final 4 months the feasibility data will be analyzed along with feedback from patients and therapists. This data will be used to revise the protocol for training therapists to use *Anxiety Coach*, prepare a manuscript for publication, and apply for R01 funding to conduct a fully powered randomized controlled trial to evaluate the symptom improvement and cost-efficiency of using *Anxiety Coach* to provide minimal contact care and disseminate evidence-based treatment.

C.4. Participant Availability and Recruitment. The outpatient mental health therapists in Trial 2 will be recruited and will subsequently recruit their own patients into the study. The therapists will be provided an iPod Touch for participating in the study that they can keep. Before recruiting patients, therapists will complete appropriate training in research ethics. Patients will be recruited by the therapists during their initial evaluation. Patients will be screened and consented by study staff. Patients **and therapists** in each condition will be reimbursed for completing study assessments and recordings (\$100 total) and will receive an iPod Touch that they can keep. Partnering institutions in the minimal contact condition can be reimbursed for non-billable time spent on the *Anxiety Coach* portal at a rate of \$146.34 per hour up to 6 hours. The therapists for Trial 1 have largely been recruited under the initially approved IRB protocol. Additional therapists will be recruited as needed.

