If therapists in Trial 1 choose to use Anxiety Coach in their practice during, those patients will not be engaged in any research activities. In order to use the application the patient must agree to the terms of use that explain what data Mayo Clinic collects and how these data are used.

C.7.e. Treatment Assignment. For Trial 2, therapists will be randomized to either TAU or FTF-AC after they are consented. The therapist will then offer participation to the next patient they see likely to qualify. (If needed, the second patient treated by a therapist randomized to TAU will be enrolled in the FTF-AC condition.) This format clearly differentiates the therapists' participation in the study from the patients' participation. To limit bias in enrollment, neither patients nor the independent evaluators will be aware of therapeutic condition at the time of enrollment. Treatment in each condition can begin within 1 to 2 weeks of the evaluation as soon as the patient has completed the study evaluation. All patients will be informed that participation in the study includes the possibility of enrollment into either of two conditions. If patients discontinue treatment prematurely, before the sixth session, they will not be replaced with another patient. Instead efforts will be made to complete early withdrawal post-treatment evaluations on all enrollees and the frequency of premature discontinuation will be compared between conditions. For Trial 1, the therapists will have access to the Anxiety Coach application and can use it as they choose in their clinical practice. For Trial 3, treatment assignment will occur following consent and the pre-evaluation is completed.

C.7.f. Therapists, Treatment Integrity and Competence. Therapists in Trials 2 and 3 will provide treatment. To determine the success of creating conditions with distinct therapist behavior, all sessions and communication in each condition will be recorded and coded for use of exposure and other interventions. In the TAU condition, the therapist will not receive any instruction regarding the content of treatment. In all three conditions across the two trials the intervention specialists or the PI will monitor and support the therapists' compliance with guidelines. The intervention specialists have highly developed therapeutic skills, at least five years' experience providing CBT to children with anxiety disorders and their families, extensive one-on-one

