supervision from [name], attendance of workshops on anxiety treatment, and been involved in the development of *Anxiety Coach*. [name] will train the intervention specialists in the procedures outlined in the UPM for supporting therapists, meet weekly for supervision, and provide additional supervision as needed for concerns about a therapist's use of the study interventions or a patient's progress, clinical deterioration, or development of new symptoms.

C.7.g. Assessment Timeline. Patient participants will receive two assessments conducted via videophone by a trained independent evaluator blind to condition under the supervision of [name]. The initial assessment will be conducted at baseline (Time 1) when the patient's eligibility is determined. The patient will begin treatment within one to two weeks. The patient's response to treatment will be assessed 12 weeks (+/- 2 weeks) after the initial treatment session (Time 2). The evaluations will be comprehensive in nature (e.g., diagnostic interview, clinician ratings, parent- and self-reports). Accommodations will be made for families without electronic access, such as videophone assessments in the therapist's office. Beginning at the baseline assessment and continuing throughout the study, patients will rate their daily symptoms with an iPod Touch. Therapists in Trial 1 will complete the survey materials from Phase I inquiring about treatment practices and beliefs prior to receiving training in the use of *Anxiety Coach*. Two weeks after receiving *Anxiety Coach* training the therapists will be asked to complete the same survey material plus measures assessing software usability. 6 months after the initial training, therapist will be asked to complete the survey material, usability measure, and a questionnaire about their actual use of *Anxiety Coach* since the training.

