C.10.b.2. Aim 2: Assess feasibility, safety, acceptance, and impact of *Anxiety Coach*. Analyses for Trial 1 will consist of examining changes in therapist questionnaires via repeated measures analyses of variation and descriptively summarizing data on therapist use and ratings of acceptability. Most appropriately for the present design of Trials 2 and 3, descriptive statistics will be calculated on all fidelity (e.g., frequency of exposure), feasibility (e.g., quantity and content of communication between the therapist and project director, frequency of assessing the application), and clinical variables (e.g., means, standard deviations, percentage of patients continuing to meet diagnostic criteria). Consistent with the ultimate goal of generating estimates of the effect of *Anxiety Coach*, symptom change within Trials 2 and 3 will be compared between groups using repeated measures analysis of variance (RMANOVA) and the frequency of the therapists' use of exposure will be compared between the TAU and FTF-AC condition using analysis of covariance (ANCOVA) to control for diagnosis and symptom severity. Given that this project aims to test the feasibility of a fully powered RCT, analyses testing group differences will be considered exploratory. Although the use of RMANOVA and ANCOVA has significant limitations (i.e., the treatment of missing data), the small sample size and inclusion of multiple therapists does not permit the use of a more powerful statistical approach such as a mixed-effects regression model. However, exploratory analyses using mixed-effects regression model will be conducted. These analyses will be completed to assist in planning design and analysis of a fully powered RCT, rather than to provide interpretable results.

C.10.b.3. Aim 3: Develop a protocol for implementing *Anxiety Coach*. To develop a protocol for using *Anxiety Coach* to increase therapist fidelity to evidence-based CBT and provide treatment with minimal direct contact, the frequency and timing of contact between the project director and therapists as well as the therapist and patient will be used to construct guidelines for monitoring and interacting with therapists and patients. The questions from patients and therapists will be summarized qualitatively and used to refine *Anxiety Coach* and develop the educational component of the protocol.

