C.10.c. Attrition, Noncompliance and Missing Data. The intention to treat analysis set will serve as the principal analysis set. Attempts will be made to minimize the missing data due to missed visits (i.e., fewer than the required six appointments). To handle missing data the following approach will be used. The analyses of the primary outcome will be performed in two ways: 1) using complete case scenario i.e., those patients that

July 1, 2019 (Version 12)

have data available on both time points and 2) imputing a rank from the earlier time point carried forward. Last rank carried forward has been shown to have better statistical properties than the last observation carried forward approach. In addition to these, we will also explore other sensitivity analysis such as imputation of a mean or median or worst or best case values in the respective groups. Findings from sensitivity analysis will be viewed in light of primary analysis prior to reaching final conclusions and interpretation of the results.

PROTECTION OF HUMAN SUBJECTS

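### With two assessments, the planned RMANOVA of symptoms is a change-score test: Trial 3 should estimate the effect adjusted for baseline, and Trial 2 should show both estimates with neither leading.

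*Protocol*

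**What the plan says.** For symptoms, protocol C.10.b.2 states that "symptom change within Trials 2 and 3 will be compared between groups using repeated measures analysis of variance (RMANOVA"). It gives the purpose as producing effect estimates and calls tests of group differences exploratory. ANCOVA is planned there only for therapists' use of exposure, so no baseline-adjusted symptom estimate is specified.

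C.7.g (Assessment Timeline) says: "Patient participants will receive two assessments conducted via videophone by a trained independent evaluator blind to condition". These fall at baseline and 12 weeks (plus or minus 2). C.9 gives the other study measures the same pre/post schedule, with stated exceptions. The daily ratings on the iPod Touch run throughout the study.

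C.10.c makes intention to treat the principal analysis set and continues: "The analyses of the primary outcome will be performed in two ways". The first way is complete case. The second is "imputing a rank from the earlier time point carried forward". Other imputations follow as sensitivity analyses. Section 4.1.2.b adds that everyone randomized to a treatment condition is to be included in the analyses.

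The two trials assign treatment differently:
- Trial 3 (C.3.b): "children with anxiety disorders will be randomized to receive with MC-AC". C.7.e gives the timing: "For Trial 3, treatment assignment will occur following consent and the pre-evaluation is completed". Aim 2 gives the size: "with minimal contact (N = 30 patients").
- Trial 2 (C.7.e): therapists are randomized once they have consented. "The therapist will then offer participation to the next patient they see likely to qualify". If needed, the second patient of a therapist randomized to TAU goes to FTF-AC.

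The SAP is descriptive. It contains no between-group model and no missing-data rule, so this point rests on the protocol.

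**The concern.** With one baseline and one follow-up, RMANOVA uses baseline in one fixed way: it subtracts all of it. If the true slope of follow-up on baseline is below 1, an arm that starts worse by chance appears to improve more, and that excess goes into the group estimate. C.3.c says the data will support an application for a fully powered trial. What is at stake is therefore the size of one planning estimate, not a significance claim.

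Two related matters need care. In Trial 2 a baseline difference need not be chance, so the choice between adjusted and change-score estimates depends on something the data cannot show. In C.10.c, with two waves, the earlier time point can only be baseline, which decides what carrying a rank forward does to a patient with no Time 2 score.

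**Working it through.** **Inputs.** From the protocol: two assessments (C.7.g), 30 patients in Trial 3 (Aim 2), and CY-BOCS SDs of 5.0 before treatment, 6.4 just after and 7.5 four months later in a series of 15 youths with OCD (C.2.b). Assumed, because the documents do not give them: 15 per arm, pre/post correlation r of 0.3 to 0.7, dropout of 10 to 30%, and a Trial 2 selection difference of 0.3 or 0.5 SD. The plan has no power or effect-size figure to reproduce.

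**1. Identity.** With two waves the group-by-time contrast is the difference between arms in mean (Time 2 − Time 1), and its error term is the within-arm variation of that change. So F(1, N−2) = t² for change, the same as regressing Time 2 on group with the baseline slope set to 1. In 200 simulated datasets of 15 versus 15, the largest gap between F and t² was 3e-15. This concerns the group-by-time term for pre/post measures, not the daily ratings.

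**2. Trial 3, chance imbalance.** The SE of the baseline difference is √(2/15) = 0.365 baseline SD. A difference at least that large, in either direction, arises in 32% of trials. Given a baseline difference D, the change-score estimate is displaced by (r·s1/s0 − 1)·D, where s0 and s1 are the SDs at Time 1 and Time 2. For D = 0.365, in baseline SD:

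| SDs (s0/s1) | r = 0.3 | r = 0.5 | r = 0.7 |
|---|---|---|---|
| equal | −0.256 | −0.183 | −0.110 |
| 5.0/6.4 | −0.225 | −0.131 | −0.038 |
| 5.0/7.5 | −0.201 | −0.091 | +0.018 |

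Simulation check with equal SDs: 200,000 trials, keeping the 13,149 with D between 0.315 and 0.415 (mean 0.363). The change score was displaced by −0.251, −0.177 and −0.107, and ANCOVA by 0.003, 0.004 and 0.001. Averaged over all randomizations, both methods recovered an assumed effect of 0.80 SD.

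**3. Trial 3, precision.** The variance ratio of ANCOVA to change is s1²(1 − r²) / (s0² + s1² − 2·r·s0·s1), times 1 + 1/(N − 4) = 27/26 for estimating the slope at N = 30:

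| SDs (s0/s1) | r = 0.3 | r = 0.5 | r = 0.7 |
|---|---|---|---|
| equal | 0.675 | 0.779 | 0.883 |
| 5.0/6.4 | 0.828 | 0.939 | 1.025 |
| 5.0/7.5 | 0.905 | 1.001 | 1.036 |

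The first factor cannot exceed 1, so the worst case is 27/26 = 1.038.

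**4. Trial 2, systematic difference.** Take no treatment effect, equal SDs, r = 0.5 and a baseline difference d. If the difference persists unchanged, change is right and ANCOVA is off by (1 − r)d: 0.15 SD for d = 0.3 and 0.25 SD for d = 0.5. If it fades to r·d, ANCOVA is right and change is off by the same amounts with the opposite sign. Two waves cannot distinguish these cases.

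**5. Missing Time 2 scores.** In an analysis on ranks, a patient whose baseline rank is carried forward has a rank change of 0. With a random fraction m missing, the group effect becomes (1 − m) times its full size: 0.90, 0.80 and 0.70 at 10, 20 and 30%. Simulation (20,000 runs per rate, ranks scaled within wave) gave 0.896, 0.793 and 0.688. If dropouts truly keep their baseline rank, carrying it forward is exact and complete case overstates by about 1/(1 − m): 1.11, 1.25 and 1.43, against 1.116, 1.260 and 1.449 in simulation.

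**The case against.** The strongest reply is that Trial 3 contains no error. The change score is unbiased over randomization. The displacement is conditional on an imbalance of chosen size, and it is only part of the estimate's own uncertainty: with equal SDs, 0.256/0.432, 0.183/0.365 and 0.110/0.283, or about 0.6, 0.5 and 0.4 of its SE. With the only SDs the protocol supplies, ANCOVA may gain no precision. All of this stands. What remains is that baseline is measured before assignment, adjustment removes a displacement that can be seen in the trial's own data, and its cost is capped at about 4% of variance.

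C.10.b.2 also concedes that RMANOVA has limitations and adds exploratory mixed models. The limitation it names is the handling of missing data, not the fixed slope. The mixed models are offered as an aid to planning rather than for interpretation, so they do not settle which estimate is reported.

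For Trial 2, the protocol has safeguards: the offer goes to the next likely patient, and an evaluator blind to condition determines eligibility (C.7.d). These limit selection but do not exclude it, because C.7.e says only that patients and evaluators are unaware of condition at enrolment. A reader might infer that Trial 2 selection is biased. The documents show only that it could be.

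A reader might also want to demote last rank carried forward and lead with patients who have Time 2 data. That sits badly with the commitment in 4.1.2.b to include everyone randomized, and it exchanges possible shrinkage for possible overstatement. C.7.e plans early-withdrawal evaluations, which may keep the problem small.

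**Conclusion.** The point holds as a modest improvement to consider. For pre/post symptom scores the planned test is a change-score test. In Trial 3 a one-SE chance imbalance moves the estimate by 0.26, 0.18 or 0.11 SD at r = 0.3, 0.5 and 0.7, given equal SDs and 15 per arm. With the C.2.b SDs the movement is smaller and can be close to nil.

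Three stronger readings are not supported:
- That the Trial 3 RMANOVA is biased. Assignment follows the baseline evaluation, so over randomization it is not.
- That ANCOVA will be more precise. The ratio runs from 0.675 to 1.036 across the cases shown, and the unequal SDs come from a small OCD series.
- That one method should lead in Trial 2. Either can be off by 0.15 to 0.25 SD under the stated assumptions.

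The last-rank figures apply only if the analysis is run on ranks. C.10.c neither states this nor names the primary outcome. Consequences are limited because C.10.a calls the analysis primarily descriptive and the study is not powered for group differences.

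**What to change.** **C.10.b.2, Trial 3.** Suggested wording:

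> For each symptom score measured before and after treatment, the group effect will be estimated by ANCOVA of the Time 2 score on group and baseline score, with a 95% confidence interval, as an exploratory analysis. RMANOVA will be secondary.

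**C.10.b.2, Trial 2.** Suggested wording:

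> Change-score and baseline-adjusted estimates will be reported side by side as descriptive results, and neither will be the lead estimate. Second patients of TAU therapists who are placed in FTF-AC will be identified separately as not randomized. Two patients of one therapist will not be treated as independent.

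**C.10.c.** Keep both listed analyses, so that all randomized patients stay represented as 4.1.2.b requires, and add:

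> With two time points and an analysis on ranks, carrying the rank forward gives a patient without a Time 2 score zero rank change. Under random dropout this shrinks the rank effect by roughly the missing fraction. Complete case can overstate the effect if dropouts keep their baseline rank. The two results will be shown together.

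The daily ratings, the other sensitivity analyses and the exploratory mixed models are unaffected.

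**Cost.** A few sentences and a few lines of code, with no new data and no change to the SAP. Trial 3 gives up one degree of freedom and at worst about 4% in variance at N = 30. Readers of Trial 2 get two estimates instead of one. Showing both does not cure any selection in Trial 2.

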Trial 1. In Trial 1 (Acceptability) we will gather acceptability and usability data from up to 30 therapists. After being consented therapists will complete a packet of information about how they treat child anxiety and their beliefs about treatment related issues. Each therapist will then receive training from a study intervention specialist on how to use Mayo Clinic Anxiety Coach. The therapists will be given access to use Mayo Clinic Anxiety Coach and be given an iPod Touch and can incorporate it into their practice as they desire for a period of six months during which time the therapists will have access to the intervention specialist to answer questions about how to use the application. To protect patient confidentiality, the system will generate numerical identifiers (e.g. Patient #1) and therapists will only be able to enter ages into the system, rather than full names and birthdates. Therapist will be asked to complete questionnaires about how they treat child anxiety and their beliefs about treatment related issues as well as questionnaires about usability and how they integrated Anxiety Coach into their practice two weeks and six months after completing the training. In addition, data automatically recorded through any use of the application will be analyzed.

Trial 2. In Trial 2 (Increasing Exposure Use) 30 therapists will be randomized to treat 30 children with anxiety disorders with treatment as usual or FTF-AC. (If necessary due to limited therapist availability, therapists randomized to TAU will treat a second patient with FTF-AC). Therapists and patients/parents will be consented. Data collection will include questionnaires completed by therapists, patients, and parents before and after treatment, as well as audio recordings of sessions, and data automatically saved by the application.

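### The exploratory arm-mean or arm-median fill for missing post-treatment scores counts filled values as observed, so its tests and intervals are too optimistic and it is a weak check on missing data

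*Protocol*

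**What the plan says.** Protocol C.10.c takes the intention-to-treat set as the principal analysis set and names two main analyses: "The analyses of the primary outcome will be performed in two ways: 1) using complete case scenario", and a second that carries the earlier rank forward. It then adds, as further sensitivity analyses to be explored, "imputation of a mean or median or worst or best case values in the respective groups". On their use it says: "Findings from sensitivity analysis will be viewed in light of primary analysis prior to reaching final conclusions and interpretation of the results". No variance correction or multiple imputation is mentioned.

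The test comes from C.10.b.2: "symptom change within Trials 2 and 3 will be compared between groups using repeated measures analysis of variance (RMANOVA". That section also calls the tests of group differences exploratory and plans exploratory mixed-effects regression. C.10.a says the study is not powered for group differences and that the analysis is mainly descriptive. The SAP is descriptive too and does not mention missing outcomes, so C.10.c is the only missing-outcome rule in the documents.

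**The concern.** A missing post-treatment score replaced by the mean or median of the patient's own arm is then analysed as if it had been measured. The filled patients raise the sample size but bring no new outcome information, so the calculated standard error is smaller than the real uncertainty of the estimate.

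As a robustness check the method is also weak. It assumes that patients without a post score did, on average, as well as those with one, and complete-case analysis already relies on much the same assumption. The arm's post-treatment mean does not move under mean filling and hardly moves under median filling.

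What is at stake is interpretation. C.10.c has these results read together with the primary analysis before conclusions are drawn. A filled analysis shows the full randomized number and usually a tighter interval, so it can look like confirmation. The pilot is also meant to supply effect estimates for a fully powered trial, and a standard deviation taken from filled scores would be a poor basis for that trial's sample size.

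**Working it through.** **Inputs from the documents**
- Trial 2 (C.3.b): "30 therapists will be randomized to treat 30 children with anxiety disorders with treatment as usual or FTF-AC". Trial 3 (Specific Aims, Aim 2): "with minimal contact (N = 30 patients". Each has two conditions.
- Two assessments, baseline and 12 weeks (C.7.g). Baseline determines eligibility, so only the post score should be missing.
- Planned test: repeated-measures ANOVA on symptom change (C.10.b.2). With two time points, the group-by-time test is a t-test on change.

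**Assumptions, because the documents give no figure**
- n = 15 per arm. No allocation ratio is stated, and a TAU therapist's second patient may go to FTF-AC.
- Two-sided alpha of 0.05, no true effect, scores missing completely at random, equal variances.
- Missing rate of about 10% to 30%, with fixed counts of 1 to 5 of 15 per arm (7% to 33%).
- Pre-post correlation ρ from 0.3 to 0.8.

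The plan has no error-rate figure of its own to reproduce.

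**Step 1: the analysed score itself is filled with the arm mean.** With k of n observed per arm, filling multiplies the within-arm variance by (k−1)/(n−1) and divides it by n instead of k. Hence

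SE ratio (filled / complete-case) = √[k(k−1) / (n(n−1))]

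true level = 2·P(T with 2k−2 df > t(0.975, 2n−2) × SE ratio), where t(0.975, 28) = 2.048.

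Example with 3 of 15 missing: √(12·11 / (15·14)) = √(132/210) = 0.793. The effective cut-off is 2.048 × 0.793 = 1.624 on 22 df, so the true level is 11.9%.

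| Missing per arm | SE ratio | True level |
|---|---|---|
| 1 of 15 | 0.93 | 6.8% |
| 2 of 15 | 0.86 | 9.0% |
| 3 of 15 | 0.79 | 11.9% |
| 4 of 15 | 0.72 | 15.4% |
| 5 of 15 | 0.66 | 19.7% |

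Median filling is nearly the same by simulation: 12.0% at 3 of 15 and 20.1% at 5 of 15. With random dropout of 10%, 20% and 30%, simulated levels for mean filling are 7.9–8.3%, 12.0–12.9% and 18.0–18.6%. These ranges cover a t-test on the post score, ANCOVA, and a change score that is itself filled.

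**Step 2: the planned test, with only the post score filled and change then analysed.** A filled patient's change is the arm's observed post mean minus that patient's own baseline, so it still varies. With score variance 1, per arm:
- expected variance of the filled changes: V = 1 + [(k−1)/(n−1)]·(1−2ρ)
- squared SE that the analysis reports: V/n
- true variance of the mean change: 1/k + 1/n − 2ρ/n
- squared SE in the complete-case analysis: 2(1−ρ)/k

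With 3 of 15 missing:

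| ρ | V/15 | Complete-case | True | Filled SE / complete-case SE | Filled SE / its true SE |
|---|---|---|---|---|---|
| 0.3 | 0.0876 | 0.1167 | 0.1100 | 0.87 | 0.89 |
| 0.5 | 0.0667 | 0.0833 | 0.0833 | 0.89 | 0.89 |
| 0.7 | 0.0457 | 0.0500 | 0.0567 | 0.96 | 0.90 |
| 0.8 | 0.0352 | 0.0333 | 0.0433 | 1.03 | 0.90 |

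The filled SE is not always below the complete-case SE; at ρ = 0.8 it is slightly above it on average. In every row it is about 10% below the true SE of the filled estimate, and that gap is what inflates the test.

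Simulated levels for this test (100,000 runs per setting, ρ = 0.3 to 0.8):

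| Missing per arm | Mean fill | Median fill |
|---|---|---|
| 2 of 15 | 6.2–6.8% | 6.3–6.9% |
| 3 of 15 | 7.3–7.8% | 7.6–8.0% |
| 5 of 15 | 9.7–10.7% | 10.5–11.1% |

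With random dropout of 10%, 20% and 30% (mean fill, ρ = 0.3 to 0.7) the levels are 6.0–6.4%, 7.7–8.2% and 9.7–10.5%. Complete-case analysis of the same data gives 4.9–5.1%, so the excess comes from the filled values.

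**Step 3: effect on planning.** If the standard deviation of mean-filled post scores were used to size the next trial, the variance would be multiplied by 11/14 = 0.79 with 3 of 15 missing, and the sample size would be about 21% too small. The documents do not say that it would be used in this way.

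**The case against.** The strongest reply is that this is a minor part of the plan. The main analyses are complete-case and last rank carried forward. Mean and median filling are examples of what may be explored, and they are to be read in the light of the primary analysis. The study is unpowered and mainly descriptive, and its group tests are labelled exploratory. All of this stands, and it limits the weight of the point. It does not make the filled intervals correct, and these results are still to be considered before final conclusions.

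A second reply is that C.10.b.2 already plans mixed-effects regression and acknowledges that its main methods handle missing data poorly. That also stands and makes the fix easier. However, C.10.b.2 presents the mixed model as an aid to planning the next trial and does not expect interpretable results from it; C.10.c does not name it as a missing-data check.

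A third reply is that multiple imputation in arms of about 15 is fragile. This is fair, and it argues for a very small imputation model.

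Two stronger readings are tempting. One is that the planned test would run at 8% to 19% or 20%. That range needs the post score alone to be tested or the change score itself to be filled; the plan specifies change, and with only post scores filled the range is about 6% to 11%. The other is that the filled analysis is always more precise than complete-case. At ρ = 0.8 the filled SE is the smaller one in only about half of simulated trials.

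**Conclusion.** The point holds in a limited form. Mean or median filling by arm, analysed as observed data, gives tests and intervals that are too optimistic, and it tells the reader little about robustness to missing outcomes.

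The sizes rest on assumptions the documents do not supply: 15 per arm, about 10% to 30% missing completely at random (up to 5 of 15) and a two-sided 5% test. On that basis the true level is about 6% to 11% for the planned analysis of change with post scores filled, and about 8% to 20% for the post score alone or a filled change score. The SE is usually, not always, smaller than the complete-case SE.

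A reader might infer that the trial's main result or a confirmatory error rate is compromised. The documents do not support that: the method is an optional sensitivity analysis, and group comparisons are exploratory throughout. The worst-case and best-case fills in the same sentence are a separate matter, not judged here.

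**What to change.** Delete mean and median imputation from C.10.c and name one replacement as the missing-data sensitivity analysis:
- the likelihood-based mixed-effects model already planned in C.10.b.2, fitted to all randomized patients with their baseline and any available post scores; or
- multiple imputation by arm from the baseline score, combined with Rubin's rules.

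C.10.b.2 should then say that the mixed model also serves this purpose, still as an exploratory analysis. If filled results are kept, report them as point summaries only, without standard errors, standard deviations or p-values.

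The cost is a sentence or two in the protocol and a little more analysis work. Intervals will usually be wider than those from the filled data. The imputation model must stay small, with baseline score as the only predictor, because each arm has only about 15 patients.
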